- 21) Hypertension with systolic BP >160 mm Hg or diastolic BP >90 mm Hg at screening, systolic BP > 165 mm Hg or diastolic BP > 95 mm Hg immediately prior to treatment with study drug or hypotension with systolic BP < 90 or diastolic < 60 at screening or immediately prior to treatment with study drug; heart rate >110 or <60 at either of these time points;
- 22) Treatment with sildenafil (Viagra), tadalafil (Cialis), Avanafil (Stendra), Vardenafil (Levitra) or other drugs in the same category of phosphodiesterase-5 enzyme inhibitors within 2 weeks of infusion.

In no case will it be recommended to a participant to discontinue a particular treatment if there is any evidence that the treatment is providing clinical benefit. Additionally, only the patient's prescribing physician, and never the study physician, will take a patient off a medication.

If urine toxicology is positive and not explained by a prescribed medication at any point during the study, the participant will be disqualified from the study. If this occurs, the patient will be provided with a referral for drug counseling and treatment if the patient wishes to seek treatment.

As part of the initial screening, subjects will be asked to provide emergency contact information, and their consent obtained to call the emergency contact to confirm that they are willing and able to serve as such.

Finally, a capacity evaluation will be conducted by an independent psychiatrist in order to ensure sufficient subject understanding of the potential risks and benefits of participating in the study.

 Mount Sinai	Protocol Title:	Pharmacologic attenuation of ketamine using nitroprusside
	Principal Investigator Name/Contact Info:	[name]/ [contact]
	Primary Contact Name/Contact Info	[name] / [contact]
	Date Revised:	4/15/2019
	Study Number:	HSM#16-00928/GCO#16-1580

c) Number of Subjects

Our goal is for 40 individuals to be randomized in this study. Based on our expected screen fail rate, we expect to enroll approximately 100 patients who will sign the consent for and be screened for study eligibility.

d) Study Timelines

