Subjects undergo a screening period that may last up to four weeks (Visit 0). Eligible subjects then undergo the PLC/KET Test Infusion (Visit 1) and undergo evaluation of treatment response 24 hours following the infusion (Visit 2). For subjects who meet criteria to continue in the study, they are randomized to one of two treatment conditions (PLC/KET or NP/KET) to take place up to four weeks from the Test Infusion (Visit 3). Subjects will again return for evaluation 1 week (+/- 2 days) following Visit 1(Visit 2a). After the second infusion (Visit 3), subjects will return for evaluation at 24 hours (Visit 4) and 1 week (+/- 2 days) following Visit 3 (Visit 5). Subjects will return for a final exit visit (Visit 6) 14 days (+/- 2 days) following the second infusion (Visit 3). Therefore, the total study participation time will be up to 10 weeks.

We anticipate a 2-year project period, during which time approximately 100 patients will be screened, with 40 patients randomized. However, after 8 patients have completed the study, the results will be unblinded to an independent statistician and an interim analysis conducted. On this basis, the study may be terminated, or it may be continued towards the goal of randomizing 40 total patients. A second interim analysis will be conducted once the sample size has doubled, and 16 patients have completed the study. The statistician will receive de-identified coded data only.

e) Study Endpoints

Primary Outcomes

- (a) Change in Montgomery–Asberg Depression Rating Scale (MADRS) compared across PLC/KET and NP/KET administrations.
- (b) Change in four-item positive symptom subscale of the Brief Psychiatric Rating Scale (BPRS), Clinician-Administered Dissociative States Scale (CADSS) and Visual Analog Scale (VAS) scores from Time 0 to Time 40 minutes compared across PLC/KET and NP/KET administrations.

 Mount Sinai	Protocol Title:	Pharmacologic attenuation of ketamine using nitroprusside
	Principal Investigator Name/Contact Info:	[name]/ [contact]
	Primary Contact Name/Contact Info	[name] / [contact]
	Date Revised:	4/15/2019
	Study Number:	HSM#16-00928/GCO#16-1580

Secondary Outcome

Change in molecular profiles obtained from blood draws of subjects at set time points that parallel clinical ratings during infusions of the agents under investigation and post-infusion follow up.

Statistical Analysis

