Study drugs are administered on Study Visits 1 (single-blind) and 3 (double-blind). Visits 1 and 3 will occur up to four weeks apart to allow subject depression levels to return to baseline, a necessary component of the study design in order to test whether NP has any effect on the antidepressant action of KET. At Visit 1, participants will receive single-blind placebo (PLC) followed by KET (0.5 mg/kg/hour for 40 minutes), in which they are blind to the PLC/NP condition but are aware they are receiving KET. Subjects return to the clinic 24 hours following Visit 1, at which time their eligibility to continue and be randomized in the study is determined. The criteria for continuing is a significant antidepressant response to KET as demonstrated by MADRS score of $\geq 50\%$ improvement from baseline. Eligible subjects are randomized to one of two treatment conditions for Visit 3 (double-blind): PLC/KET or NP/KET (NP dose: 0.5 micrograms/kg/minute for 240 minutes), where again, the blinded condition is PLC/NP, but the subjects are aware they are receiving KET. Ineligible subjects (i.e., ketamine non-responders) will be scheduled to return to the clinic for an exit visit 1 week (7 ± 2 days) following the first infusion. The appearance of the nitroprusside will be protected to allow this drug to be blinded. Given the potential lengthy duration between visits (between 2 and 4 weeks), subjects will return to the clinic approximately 1 week (7 ± 2 days) following V1 (PLC/KET) for a check-in (Visit 2a) with the study doctor in order to ensure subject safety, as well as to be evaluated for remission of depressive symptoms. Additionally, a phone call MADRS will be administered 3 to 4 days following the in-person check-in, which will serve as the final determinant of the subject's return to baseline (defined as receiving a score within 20% of the baseline MADRS). If the subject has not returned to baseline, the V3 will be rescheduled for a date approximately two weeks following its initial appointment in order to allow maximum time (4 weeks) for a return to baseline, and the two check-ins (Visit 2a and by-phone check-in) will be repeated for the next two weeks, for a total of 4 additional check-ins. Following the V3 infusion visit, subjects again return to the clinic at 24 hours (Visit 4) and at 7 ± 2 days (Visit 5) following the second infusion day, and once more 14 ± 2 days after the infusion for the Exit Visit (Visit 6).

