- *Blood draws before/after infusion (if applicable)*
- *Clinical ratings before/during/following infusion*

Study Visit 1 will occur up to 4 weeks after Study Visit 0. At this Visit, all participants will first receive PLC for Infusion 1 and KET for Infusion 2. Details of the dosing and timing for these infusion sequences, as well as the associated clinical ratings and blood draws, is explained in the “Description of Study Drug Procedures” section above.

Study Visits 2 and 4 (24-h follow ups)

Participants will return to the study site 24 hours after Study Visit 1 for Study Visit 2. At this visit, safety and efficacy assessments will be performed (no drugs will be administered). The research team will analyze the outcomes of the MADRS and CADDs for each participant obtained on this day. In order to best assess the capacity of NP to attenuate the pro-psychotic and antidepressant effects of KET, only those participants who show improvement in MADRS $\geq 50\%$ compared to baseline will be eligible to return for Study Visit 3.

 Mount Sinai	Protocol Title:	Pharmacologic attenuation of ketamine using nitroprusside
	Principal Investigator Name/Contact Info:	[name]/ [contact]
	Primary Contact Name/Contact Info	[name] / [contact]
	Date Revised:	4/15/2019
	Study Number:	HSM#16-00928/GCO#16-1580

Participants who meet these criteria will return for Study Visit 3 up to 4 weeks later (depending on the amount of time required for the patient's MADRS score to return to baseline). These participants will be randomized to receive a drug administration sequence of either PLC/KET or NP/KET at Study Visit 3.

All patients who return for Study Visit 3 will return to the study site within 24 hours for Study Visit 4. At this visit, safety and efficacy assessments will be performed (no drugs will be administered).

Study Visits 2a and 5 (7-day follow-ups) and Phone Call Check-In

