 Mount Sinai	Protocol Title:	Pharmacologic attenuation of ketamine using nitroprusside
	Principal Investigator Name/Contact Info:	[name]/ [contact]
	Primary Contact Name/Contact Info	[name] / [contact]
	Date Revised:	4/15/2019
	Study Number:	HSM#16-00928/GCO#16-1580

structured interview that uniquely measures the full spectrum of suicidality including passive and active suicidal ideation, suicidal intent as well as suicidal behaviors. Subjects will be assessed at every visit with the CSSRS by a study clinician. Any subject with an increase in suicidality and all those subjects found to have a plan or intent will undergo thorough assessment by the study psychiatrist who will determine the appropriate course of action, including whether acute intervention is needed and whether it is in the best interest of the subject to continue in the study. If necessary, the study psychiatrist will seek consultation from the study PI or medical monitor. If continued participation is deemed not to be in the best interest of study subject, s/he will be discontinued from the study.

g) Data Management and Confidentiality

Case report forms and source documents are completed electronically using the institution's REDCap data capture system, a secure web-based application protected by Mount Sinai's server and managed by IT, which will obviate the need for data entry and data cleaning at time points separate from data capture, reducing the risk of error. The case report forms and source documents are based on established instruments or are developed from adaptations of NIH and industry-sponsored clinical trial protocols. Study data are recorded without specific patient identifying information. Patient identifiers are sequestered in a separate REDCap database. Access to both study databases is password protected and only IRB approved study members have access.

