The DSMB will ensure the safety of study participants and the integrity of the data collection in the projects. To achieve this goal, the DSMB will perform an ongoing evaluation of the safety of patients participating in the clinical outcomes in the clinical trial. This includes monitoring adverse events and overall clinical outcomes in the studies. Through this process the board will evaluate the need for study termination and/or modification of study criteria for inclusion, exclusion, or discontinuation. In

Protocol Title:	Pharmacologic attenuation of ketamine using nitroprusside
Principal Investigator Name/Contact Info:	[name]/ [contact]
Primary Contact Name/Contact Info	[name] / [contact]
Date Revised:	4/15/2019
Study Number:	HSM#16-00928/GCO#16-1580

addition, the DSMB will be responsible for the evaluation of the adherence to written protocols regarding the protection of human subjects and the assurance of identity protection as specified in the Data Sharing Section. The DSMB will expeditiously review all serious adverse events and perform ongoing scheduled reviews of non-serious adverse events and study dropouts. The DSMB includes the following members: The Oversight Committee members are to include: [name], Professor of Psychiatry, Brown University; [name], Icahn School of Medicine Professor of Anesthesiology; [name], Professor of Psychiatry, Icahn School of Medicine at Mount Sinai; and [name], Professor of Neurology and Professor of Anesthesiology, Icahn School of Medicine at Mount Sinai. The board will review the project's data and safety on bi-annual basis and report their findings to the PI.

i) Withdrawal of Subjects

Investigators may elect to withdraw the patient due to safety concern or non-adherence to the study protocol. Subjects may withdraw at any point in the study.

6) Risks to Subjects

Risks associated with NP [The following information was derived from the FDA package insert for NP (Nitropress [package insert]. Lake Forest, IL: Hospira Inc; 2014).]

The principal hazards of NP excessive hypotension and excessive accumulation of cyanide. Transient excesses in the infusion rate of NP can result in excessive hypotension, sometimes to levels so low as to compromise the

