The reported incidence of KET-induced perceptual disturbances varies from less than 5% to greater than 30% (Knox et al. 1970; White et al. 1980) and may manifest as vivid dreaming, visualization of psychedelic color, suspension in space, kaleidoscopic floating, and out-of-body experiences. Some patients describe these psychic experiences as bizarre or frightening, while others find them pleasurable, joyful, and fascinating. Indeed, KET is also known as “Special K” as a drug of abuse related to PCP. For that reason KET was placed in Schedule III of the Controlled Substance Act in 1999. Nonetheless, when perceptual disturbances occur, they are usually mild and of short duration (Green and Johnson 1990). KET administration has transient effects on symptoms, usually lasting less than 60 minutes and rarely lasting longer than 2 hours (Carpenter 1999). The perceptual disturbances may be more common in those with preexisting psychosis (Lahti et al. 1995).

Several studies have addressed the question of prolonged psychological effects in the general population secondary to its anesthetic use and concluded that KET does not place patients at a greater risk than other anesthetics (Hersack 1994; Reich and Silvay 1989; Schorn and Witwam 1980). There is no evidence in these long-term studies that individuals exposed to KET are at risk of abusing it on follow-up.

Both ourselves and others have safely used KET in a large number of psychophysiological studies in patients with psychiatric disorders as well as in healthy with doses similar to that of the present study. A meta-analysis of a number of these studies found no evidence of behavioral sensitization following repeated KET exposure (Cho et al. 2005).

7) Provisions for Research Related Injury

We have described above the potential risks of the research procedures and the safeguards that will be used to minimize risks. These include termination of research participation if it is believed that such participation endangers a patient's welfare. Monitoring procedures are used to evaluate potential side effects of treatment or of research procedures. The protocol stipulates an extensive medical and psychiatric evaluation of all patients as a condition for research participation.

 Mount Sinai	Protocol Title:	Pharmacologic attenuation of ketamine using nitroprusside
	Principal Investigator Name/Contact Info:	[name]/ [contact]
	Primary Contact Name/Contact Info	[name] / [contact]
	Date Revised:	4/15/2019

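### The withdrawal rules do not separate stopping infusions from stopping assessments, so a discontinuation after Visit 3 can end only planned follow-up

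*Combined protocol and SAP*

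**What the plan says.** Three places in the combined protocol and SAP let the team end a patient's participation on clinical grounds.

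- Section 5f, Description of Study Instruments (C-SSRS): "If continued participation is deemed not to be in the best interest of study subject, s/he will be discontinued from the study". The decision follows an assessment by the study psychiatrist. On timing: "Subjects will be assessed at every visit with the CSSRS by a study clinician".
- Section 5i, Withdrawal of Subjects: "Investigators may elect to withdraw the patient due to safety concern or non-adherence to the study protocol".
- Section 7, Provisions for Research Related Injury, lists among the safeguards "termination of research participation if it is believed that such participation endangers a patient's welfare".

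A fourth rule, in section 5b, covers unexplained positive urine toxicology: "at any point during the study, the participant will be disqualified from the study".

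On dosing, section 5f says "Study drugs are administered on Study Visits 1 (single-blind) and 3 (double-blind". Of Visit 4 it says "At this visit, safety and efficacy assessments will be performed (no drugs will be administered". Visit 5 is a meeting with the study doctor plus a MADRS. Visit 6, the exit visit, is safety and efficacy assessment, and the text has every participant returning for it. An early exit visit is described only for ketamine non-responders, about a week after the first infusion.

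Primary outcome (a) in section 5e is "Change in Montgomery–Asberg Depression Rating Scale (MADRS) compared across PLC/KET and NP/KET administrations". No time point is attached. The Statistical Analysis text names repeated measures general linear models and says nothing about missing scores or analysis sets.

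**The concern.** A withdrawal rule normally protects a patient from further exposure. Here the randomised treatment is one infusion day, and after it there is no exposure left to stop. What remains is observation. A rule that takes the patient out of the study at that stage can act only on the observation, and it does so in patients who have just shown suicidality or another safety concern.

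Two things are at stake. First, planned safety data (C-SSRS, and adverse events, which section 5h has graded at each visit) would be thinnest where they matter most. Second, worsening mood can lead to discontinuation, so whether a later MADRS score exists may depend on what that score would have been. The plan has no stated way of dealing with that.

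**Working it through.** **Step 1: what a discontinuation can remove, by timing.**

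| Discontinued | Study drug still to come | Planned assessments still to come |
|---|---|---|
| Between Visit 1 and Visit 3 | Visit 3 infusions | Visits 3 to 6 and any remaining check-ins |
| At Visit 4 (day 1) | None | Visit 5 (day 7 ± 2), Visit 6 (day 14 ± 2) |
| At Visit 5 (day 7) | None | Visit 6 |

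The C-SSRS is done at every visit, so its rule can act at Visits 4 and 5. Nothing in sections 5i or 7 limits those rules to an earlier period.

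**Step 2: follow-up lost.** From Visit 4 to Visit 6 is 14 − 1 = 13 days nominally. With the visit window it is 12 − 1 = 11 to 16 − 1 = 15 days. From Visit 5 to Visit 6 is 14 − 7 = 7 days nominally.

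**Step 3: which MADRS scores are exposed.** A decision taken at Visit 4 would probably follow that day's rating, so the 24-hour score would usually exist. The scores mainly at risk are those of Visits 5 and 6. Whether the primary result is touched depends on the unstated time point. If the repeated measures model were run on complete cases, the patient's earlier scores would drop out too; the plan does not say.

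**Step 4: illustration of size.** The plan has no figure to reproduce: it gives 40 randomised, with no SD, effect size, allocation ratio or dropout rate. Assume 1:1 allocation, so 40 / 2 = 20 per arm. Let *k* patients be lost from one arm, and let each have scored *g* points above the mean *m* of those who remain.

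- Full-arm mean = [(20 − *k*)·*m* + *k*·(*m* + *g*)] / 20 = *m* + *k*·*g* / 20.
- Observed mean = *m*, so the arm is understated by *k*·*g* / 20.

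| *k* lost | *g* = 12 | *g* = 6 |
|---|---|---|
| 2 | 1.2 | 0.6 |
| 3 | 1.8 | 0.9 |
| 4 | 2.4 | 1.2 |

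Both *g* and *k* are assumptions. Equal losses of the same kind in both arms would cancel in the difference between arms.

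**Step 5: the extreme case.** A simulation assumed a true difference of 0.90 SD, 20 per arm, a two-sided 5% t-test, and loss of exactly the worst scores from NP/KET only. Losing 1, 2 or 4 patients reduced the observed difference to 0.80, 0.72 or 0.57 SD, and power from about 79% to 71%, 63% or 45%. This is an unfavourable case, not a forecast.

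**Step 6: the text on who returns.** The Visit 6 text has every participant coming back. The withdrawal text has some leaving the study. Neither refers to the other, so a site cannot tell whether a patient discontinued at Visit 4 is still expected at Visit 6.

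**The case against.** The case against is substantial, and much of it stands.

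- **Removal is not automatic.** The C-SSRS rule follows a psychiatrist's judgement, and section 5i is permissive. If Visits 4 to 6 are only monitoring, a psychiatrist may seldom find attendance harmful. This limits how often the rule would bite; it does not change what the rule does when used.
- **A reader might infer that safety care stops.** The documents do not support that. Section 5f provides for acute intervention, section 7 for an on-call physician between visits, and section 5h for monitoring of dropouts and DSMB review. No sentence forbids later assessment. What may end is the planned research follow-up.
- **A reader might infer that the toxicology rule also removes patients after Visit 3.** Its wording reaches that far, but apart from screening the only tests described are on infusion days. Table 1, cited in section 5f, is not in the text I worked from, so a later test cannot be assumed. A positive test or non-adherence also need not mark a poor mood outcome.
- **A reader might infer a bias towards finding no attenuation by NP.** That needs more removals in NP/KET. Hypothesis I predicts less improvement, not new suicidality, and no rule removes a patient after Visit 3 for a high MADRS. Patients must be back within 20% of baseline before Visit 3, so a blunted response may simply mean staying there. Losses mainly in PLC/KET would bias the other way.
- **The gap before Visit 3 is narrow.** Responders have Visit 2a at 7 ± 2 days, the same timing as the non-responders' exit visit.

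What survives is that the rules, as written, end assessments when no drug is left to withhold, and the Visit 6 text does not fit with them.

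**Conclusion.** The point holds as a defect in how discontinuation is defined. After Visit 3, discontinuing a patient under sections 5f, 5i or 7 withholds no study drug and gives up planned C-SSRS, adverse-event and MADRS assessments, nominally up to 13 days of them. It conflicts with the Visit 6 text.

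Because suicidality and safety concerns can be related to outcome, MADRS scores at Visits 5 and 6 may be missing not at random. The direction and size of any resulting bias are not determined by the documents. The 1.2 to 2.4 point range rests on 20 per arm, losses of 2 to 4 from one arm only, and a 12-point gap; it shrinks in proportion for a smaller gap. Primary outcome (b), rated on the infusion day, is not affected by a later discontinuation, unless a complete-case analysis drops the patient altogether. The conclusion rests on the clinical-judgement rules and does not need the toxicology rule.

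**What to change.** Leave every clinical trigger and the study psychiatrist's judgement as they are. Change only what happens to data collection afterwards.

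1. In the C-SSRS text of section 5f and in section 5i, add that a patient discontinued after the Visit 3 infusion is asked to continue the assessments already scheduled at Visits 4 to 6, with consent and where the study psychiatrist judges it appropriate.
2. Reconcile this with the Visit 6 text, so that it is clear who is expected at the exit visit.
3. Offer an infused responder who is discontinued before Visit 3 an exit assessment of the type already given to non-responders, unless Visit 2a has served that purpose.
4. Record the reason and date of discontinuation and any new treatment with its start date, so that later scores can be flagged.
5. In the Statistical Analysis text, state the primary MADRS time point and how scores that are still missing will be handled.

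The cost is mainly protocol wording. No visit is added after Visit 3, and at most one for a patient leaving before it. The small downside is that some later ratings will follow newly started treatment and will need flagging.
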